Statistical considerations	
Populations for analyses
 
The following populations will be used for the statistical analyses:
 
 • Safety set: all patients who take the study preparation, even only partially. • Modified Safety set: all patients who take the study preparation, even only partially, and who do not meet significant protocol violations that regard inclusion/exclusion criteria. • PK population (only for the pharmacokinetic sub-study): all randomized patients who complete the mannitol treatment and have at least one PK assessment, regardless of the outcome of colonoscopy.

	
• Full Analysis Set (FAS): all randomized patients who take the study preparation, even only partially, undergo colonoscopy, and have a BBPS available for at least one colon segment after standard washing and air insufflation for luminal distension.• Per protocol (PP): all randomized patients who meet the following criteria:
◦ Treatment with the study drug completed.◦ Colonoscopy completed adequately in the absence of pathological obstruction that prevents reaching the right colon, including cecum, (i.e. endoscope does not find obstacles other than faecal material), and without acute deterioration of general conditions causing the suspension of the procedure.◦ BBPS and H₂ and CH₄ measurement are available for all colon segments after standard washing and air insufflation for luminal distension.◦ No significant protocol violations that regard inclusion/exclusion criteria or that can impact evaluations.

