4.1.1 PHASE II

The parallel-group dose-finding phase will be conducted at approximately 8 centres and will involve 150 patients randomly assigned (1:1:1 ratio) to one of the following three treatment groups:

- 50 g mannitol powder to be dissolved in 500 ml of water
- 100 g mannitol powder to be dissolved in 750 ml of water
- 150 g mannitol powder to be dissolved in 1000 ml of water

Of note, these doses of mannitol have been selected as this range includes the minimum (50 g) and maximum (150 g) mannitol doses used effectively in the proposed indication, as reported in published literature. Please refer to [Section 2.1](#) for further details.

Randomization is stratified by centre and by the presence of constipation (yes/no), defined as the recurrent use of laxatives or Bristol Stool Form Scale (BSFS) < 3 in the two weeks prior to randomisation.

To limit patient exposure to an ineffective dose causing repetition of colonoscopy, the adequacy of bowel cleansing will be monitored continuously and enrolment in a treatment group will be discontinued as soon as 25% of treated patients present inadequate bowel cleansing causing repetition of colonoscopy. The stopping rule, mainly guided by clinical considerations, will be applied in each treatment group as follows:

- Up to the 25th enrolled patient, enrolment in a treatment group will be stopped as soon as 6 patients present inadequate bowel cleansing causing repetition of colonoscopy (i.e. if among the initial 15 patients enrolled in a treatment group, 6 need to repeat the cleansing procedure, the treatment group will be immediately discontinued).
- From the 26th enrolled patient on (if treatment was not discontinued earlier), enrolment will be stopped as soon as 25% of patients present inadequate bowel cleansing causing repetition of colonoscopy (i.e. if among the initial 32 patients enrolled in a treatment group, 8 need to repeat the cleansing procedure, the treatment group will be immediately discontinued).

The appropriate mannitol dose to be used in the comparative non-inferiority phase (phase III) will be singled out at the end of dose-finding based on the following criteria:

- 75% or greater rate of adequate bowel cleansing.

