9.3 POPULATIONS FOR ANALYSES

The following populations will be used for the statistical analyses:

- Safety set: all patients who take the study preparation, even only partially. Patients will be analysed according to the study drug dose actually received.
- Modified Safety set: all patients who take the study preparation, even only partially, and who do not meet significant protocol violations that regard inclusion/exclusion criteria. Patients will be analysed according to the study drug dose actually received.
- PK population (only for the pharmacokinetic sub-study): all randomized patients who complete the mannitol treatment and have at least one PK assessment, regardless of the outcome of colonoscopy. Patients will be analysed according to the study drug dose actually received.
- Full Analysis Set (FAS): all randomized patients who take the study preparation, even only partially, undergo the colonoscopy, and have a BBPS available for at least one colon segment after standard washing and air insufflation for luminal distension. According to the Intention to Treat (ITT) principle, patients will be analysed according to the study drug dose assigned at randomization.
- Per protocol (PP): all randomized patients who meet the following criteria:
 - Treatment with the study drug completed.
 - Colonoscopy completed adequately in absence of pathological obstruction that prevents reaching the right colon, including the cecum (i.e. endoscope does not find obstacles other than faecal material) and without acute deterioration of general conditions causing procedure suspension.
 - Bowel cleansing assessment and gas measurement are available for all colon segments after standard washing and air insufflation for luminal distension.
 - No significant protocol violations that regard inclusion/exclusion criteria or that can condition evaluations.

Patients will be analysed according to the study drug dose actually received.

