9.4.1 ANALYSIS OF VARIABLES

Phase II - Dose finding

Efficacy

The appropriate mannitol dose to be used in the comparative non-inferiority phase (phase III) will be singled out at the end of dose-finding based on the following criteria:

- 75% or greater rate of adequate bowel cleansing.
- Rate of patients in safe conditions, defined as the absence of potentially dangerous levels of H₂ and CH₄ in each colon segment (right, between ileocecal valve and appendix or as close as possible to the ileocecal valve in case of obstacles that prevent reaching the valve; transverse, including flexures; and left at the sigmoidal-rectum junction, 15-25 cm from anal margin) after standard washing and air insufflation for luminal distension).
- Clinical judgment based on the caecal intubation rate, the incidence of adverse events, treatment adherence and acceptability (considering ease of use, taste and willingness to reuse the preparation).

Should two or all three doses prove to be equally safe and effective, the lowest dose will be selected for phase III of the study.

Descriptive statistics and Wald 95% CI of the proportion of patients with adequate bowel cleansing will be provided for each dose.

In addition, a logistic regression model will be applied to assess the influence of the two stratification factors (constipation in the two weeks before the start of preparation for colonoscopy and centre) on dose response. A patient is considered a responder if he/she presents adequate bowel cleansing. In case of unbalanced enrolment among centres, a pooling approach will be adopted.

A supportive stepwise logistic regression model will also be applied to assess the influence on dose response of potential prognostic factors (i.e. age and previous unsuccessful bowel cleansing procedures) in addition to the two stratification factors. Based on the results from this model, the need to modify the stratification factors for phase III will be evaluated and the study protocol amended, if needed.

No between-group comparisons will be performed. The decision on the dose to be selected for phase III will be made on the basis of descriptive statistics and corresponding 95% CIs and on the

results of the logistic regression models. Endpoints will be analysed on the PP population. Results from the FAS will be used as supportive.

Caecal intubation rate

Descriptive statistics and Wald 95% CI of the caecal intubation rate will be provided for each dose.

Adherence and acceptability

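### The per-protocol set can lose patients whose examination was stopped by stool, which biases the lead Phase II cleansing rate upward and lets a dose below 75% of treated patients meet the 75% criterion

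*Combined protocol and SAP*

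**What the plan says.** Section 9.3 lists the PP criteria, all of which must be met.

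- The second criterion asks for "Colonoscopy completed adequately in absence of pathological obstruction that prevents reaching the right colon", with the gloss "i.e. endoscope does not find obstacles other than faecal material", and for no acute deterioration that halts the procedure.
- The third requires that "Bowel cleansing assessment and gas measurement are available for all colon segments after standard washing and air insufflation for luminal distension". The synopsis (Section 1.1) names BBPS, H₂ and CH₄ and uses the same all-segments condition: "measurement are available for all colon segments after standard washing and air insufflation for luminal distension".

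The FAS is looser. Patients must have taken some of the preparation, undergone colonoscopy and "have a BBPS available for at least one colon segment after standard washing and air insufflation for luminal distension".

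For Phase II, Section 9.4.1 says: "Endpoints will be analysed on the PP population. Results from the FAS will be used as supportive". The first dose-selection criterion (Sections 4.1.1 and 9.4.1) is "75% or greater rate of adequate bowel cleansing". Adequacy needs a BBPS total of at least 6 and at least 2 in every segment. Under Section 8.1.1, stool that cannot be cleared is a scoreable finding, with score 0.

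No section assigns a score to a segment that stool prevented the endoscopist from reaching, and none waives the gas reading there.

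**The concern.** Take a patient whose left colon scores 0 or 1 and whose examination is stopped there because of stool. One segment below 2 already makes the result inadequate, whatever the others would have shown. The segments beyond have no gas reading and usually no BBPS, so the third criterion removes the patient from PP. This exclusion is selected on the outcome: it takes out a preparation failure that was observed, and no success can be lost because stool blocked the scope.

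The faecal-material gloss in the second criterion suggests that such patients were meant to stay. Whatever was meant, they leave the set on which the 75% criterion is read. The rate is then too high, and most so for a dose that often leaves stool behind. The Phase II caecal intubation rate, which feeds the clinical-judgment criterion and is also read on PP, is inflated for the same reason.

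**Working it through.** **Inputs.** 50 patients per dose and the normal-approximation interval (Section 9.1); the 75% criterion, PP as lead set (Section 9.4.1); the stopping rule (Section 4.1.1). The share *q* of inadequate preparations that leave PP because stool stopped the examination is not in the documents. I assume 10%, 20% and 30%.

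**The plan's own figures.** The half-width 1.96 × √(p(1−p)/50) is 12.0, 11.1 and 9.9 points at 75%, 80% and 85%. This matches the stated ±12, ±11 and ±10.

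**How many exclusions move a dose over the line.** If *a* of 50 treated patients are adequate and *k* failures leave PP, the PP rate is a/(50 − k). It reaches 75% when k ≥ 50 − a/0.75. With all 50 counted, the lowest passing result is 38/50 (76%).

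| Adequate of 50 | Failures | Exclusions needed | PP rate |
|---|---|---|---|
| 37 (74%) | 13 | 1 | 37/49 = 75.5% |
| 36 (72%) | 14 | 2 | 36/48 = 75.0% |
| 35 (70%) | 15 | 4 | 35/46 = 76.1% |
| 34 (68%) | 16 | 5 | 34/45 = 75.6% |
| 33 (66%) | 17 | 6 | 33/44 = 75.0% |

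**Chance of showing at least 75%.** The long-run PP rate is p/(1 − (1−p)q). For p = 0.70 this is 0.70/0.97 = 72.2%, 0.70/0.94 = 74.5% and 0.70/0.91 = 76.9%. The chances below are exact: binomial adequate counts, then binomial exclusions among the failures, without the stopping rule.

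| True rate | None dropped | 10% | 20% | 30% |
|---|---|---|---|---|
| 70% | 22% | 36% | 50% | 65% |
| 72% | 33% | 48% | 61% | 74% |

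**With the stopping rule.** I simulated 100,000 arms per setting at a true rate of 72%. An arm stops at 6 failures causing repetition among the first 25 patients, and after that at 25%. Excluded patients are taken to be among those who need repetition. The outcome of interest is an arm that completes with a PP rate of at least 75% while fewer than 75% of all its patients are adequate.

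| Failures causing repetition | Failures dropped from PP | Arms stopped | False pass |
|---|---|---|---|
| half | 20% | about 15% | about 24% |
| half | 30% | about 15% | about 34% |
| all | 30% | about 86% | about 0.2% |

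**Phase III.** At the margin (77% against 85%), with the same share dropped in both arms, the PP difference is 0.77/(1 − 0.23q) − 0.85/(1 − 0.15q). It shrinks from −8.0 points to −7.5, −6.9 and −6.3 points for q of 10%, 20% and 30%.

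**The case against.** **The criteria may not conflict.** A reader might infer that the second and third criteria contradict each other outright. The second criterion opens by requiring the examination to be completed adequately, and an abandoned one arguably was not. On that reading the two agree. This stands against calling it a contradiction, but not against the bias, because the same failures leave PP either way.

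**Some stool-blocked patients remain.** Section 8.1.1 lets the right-colon gas sample be taken as near the valve as obstacles allow, and a stool-filled segment that is reached can be scored 0. The loss therefore concerns examinations stopped in the left or transverse colon. For the same reason one cannot infer that caecal intubation in PP is close to 100% by construction: right-colon BBPS and gas can exist without the appendiceal orifice being seen.

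**Not every exclusion is a failure.** A fully scored patient with one missing gas reading also leaves PP, and that patient may be a success. The direction of that part is unknown. The upward bias comes from the stool-stopped examinations.

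**The stopping rule protects.** It counts treated patients, not the PP set, so it does help. It counts only failures that cause repetition, and acts only during enrolment. A tempting extreme is an arm stopped at 6 failures in 25 that shows 19/19 in PP. It does not show a wrongly passed dose, since 19/25 = 76% already meets the criterion.

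**Selection is not mechanical.** Gas safety, clinical judgment, confidence intervals, regression results and the supportive FAS also enter, and Phase III enrols new patients. A wrong dose choice is therefore possible but not automatic, and it does not by itself create a false efficacy claim.

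**Conclusion.** The point holds. As written, PP can drop known preparation failures from the lead Phase II analysis, and nothing elsewhere in the protocol repairs this. Near the threshold, one or two patients per arm are enough to carry a dose over 75%. The wider probabilities depend on two quantities the documents do not give: the share of failures stopped by stool short of the right colon, and the share that cause repetition. Depending on the second, the stopping rule leaves the problem largely in place or almost removes it.

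The caecal intubation rate on PP is inflated by an unknown amount.

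A reader might infer that Phase III is at comparable risk. The documents do not support that: Section 9.4.1 gives the FAS equal importance, and a patient with one scored segment below 2 belongs to the FAS as a failure by the endpoint definition. The shrunken PP difference is a reason to use the same corrected definition there, not evidence of a false non-inferiority claim.

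**What to change.** Amend the PP definition in Sections 9.3 and 1.1.

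1. State in both the second and the third criterion that an examination not completed, or segments not reached or not scored, because of faecal material does not exclude a patient from PP, and that the patient counts as inadequate. Changing only the third criterion would leave the completion wording free to exclude the same patients.
2. State that examinations stopped for reasons unrelated to preparation remain excluded whatever their partial scores. Keeping them only when a segment had already failed would bias PP downward.
3. Require gas readings only for the gas summaries, not for the efficacy PP set.
4. Report the Phase II caecal intubation rate on the FAS as well as on PP.

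The cost is wording. No new data are needed, and the PP cleansing rates become slightly less favourable.

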Standard proportion, π_S	0.85
Equivalence limit difference, $\pi_T - \pi_S, \Delta_0$	-0.08
Test expected proportion, π_T	0.85
Expected difference, $\pi_T - \pi_S, \Delta_1$	0
Power (%)	80
N per group	313

Sample size was computed based on normal approximation of binomial distribution without continuity correction

The non-inferiority margin $\pi_T - \pi_S = -0.08$ corresponds to a relative risk $\pi_T/\pi_S = 0.906$. Should the proportion of successes in the standard group be lower than 0.85, the non-inferiority margin will be adjusted in order to have a relative risk of at least 0.906 (e.g. if the proportion of successes observed in the standard group is 0.80, the non-inferiority margin $\pi_T - \pi_S$ will be set equal to = -0.075, corresponding to a relative risk equal to 0.906).

The total sample size (626) is adjusted to 696 patients (348 in each treatment group) considering an expected rate of dropouts and major protocol deviations of about 10% (using Freedman's formula (*Control Clin Trials*, 1990): $n' = 100*n/(100-x)$, where x is the expected percent dropout rate).

The correctness of the assumptions used to compute the sample size for phase III of the study will be re-evaluated at the end of phase II and, if needed, the sample size will be re-estimated.

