Descriptive statistics and Wald 95% CIs of the following adherence and acceptability variables will be provided for each dose:

- Adherence
- NRS score for ease of use and taste
- Willingness to reuse the preparation

Phase II - Pharmacokinetic sub-study

The pharmacokinetic parameters (C_{max} , t_{max} , AUC_{0-t} , $t_{1/2}$) of each dose will be analysed descriptively on the PK population.

Phase III - Non-inferiority

Primary efficacy analysis

The proportion of patients with adequate bowel cleansing (BBPS total score ≥ 6 , score ≥ 2 for each segment) during colonoscopy after standard washing and air insufflation for luminal distension will be calculated to evaluate the non-inferiority of the test drug vs the standard drug.

Non-inferiority will be assessed by computing the two-tailed Wald 95% confidence interval (CI) of the difference between the two proportions $\pi_T - \pi_S$. Non-inferiority is met if the 95% CI does not cross the predefined non-inferiority margin $\Delta = -0.08$ and lies entirely to the right of the margin (i.e. non-inferiority will be demonstrated if the lower bound of the two-sided 95% CI of the difference is > -0.08).

The non-inferiority margin $\pi_T - \pi_S = -0.08$ corresponds to a relative risk $\pi_T/\pi_S = 0.906$ when the proportion of successes in the standard group is 0.85. Should the proportion of successes in the standard group be lower than 0.85, the non-inferiority margin will be adjusted in order to have a relative risk of at least 0.906 (e.g. if the proportion of successes observed in the standard group is 0.80, the non-inferiority margin $\pi_T - \pi_S$ will be set equal to $= -0.075$, corresponding to a relative risk equal to 0.906).

If the 95% CI of the difference lies completely to the right of 0, the test treatment can be considered superior to the standard treatment at a 5% significance level.

The Wald method for non-inferiority of proportions will be applied (*Dann RS, 2008*).

The analysis will be performed on both the FAS and PP populations. Results from both populations will have equal importance.

Secondary efficacy analyses

The analysis of secondary variables will be performed on the FAS. No between-group inferential analysis will be performed. Descriptive statistics and 95% CIs of the between-group differences will be applied on the following variables:

- Number, appearance, size, location and histological classification of neoplastic and inflammatory colorectal lesions detected

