9.4.2 ANALYSIS OF SAFETY

Descriptive statistics both on the Safety set and on the modified Safety set for both phase II and phase III will be performed on:

- Proportion of patients with presence/absence of potentially dangerous levels of H₂ and CH₄ (>4% Vol and >100% LEL, which is equal to 5% Vol, respectively) in each colon segment during colonoscopy after standard washing and air insufflation for luminal distension.
- H₂, CH₄ and O₂ concentrations, expressed in % Vol, in each colon segment (right, between ileocecal valve and appendix or as close as possible to the ileocecal valve in case of obstacles that prevent reaching the valve; transverse, including flexures; and left, at the sigmoidal-rectum junction, 15-25 cm from anal margin) after standard washing and air insufflation for luminal distension. CH₄ (% LEL) will be converted into % Vol by means of the following formula: (CH₄ in % LEL)*5/100.
- Proportion of patients with adverse events and the number and types of events occurred.

- Proportion of patients with change from baseline (Visit 2) considered clinically significant by the Investigator of haematological and chemical parameters, where clinically significant means that the change causes an additional control or a medical intervention.
- Proportion of patients with change from baseline (Visit 2) considered clinically significant by the Investigator of vital signs (heart rate, systolic and diastolic blood pressure) (phase III only) and proportion of patients with clinically significant change of pulse oximetry and heart rate measured during colonoscopy, as well as systolic and diastolic blood pressure measured immediately prior and after colonoscopy (phase III only), where clinically significant means that the change causes an additional control or a medical intervention. Of note, clinically significant changes of blood pressure measured during colonoscopy will also be reported if considered clinically significant by the Investigator.

The analyses on the modified Safety set will be considered as supportive.

For phase III only, descriptive statistics will be provided on intestinal gas concentrations following the introduction of the colonoscope in the rectum/sigma before standard washing and air insufflation.

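### The per-protocol set requires gas readings in every colon segment, so a patient with a full BBPS but a failed gas reading is lost from a cleansing analysis that does not use gas

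*Combined protocol and SAP*

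**What the plan says.** **PP definition.** One of the PP criteria in section 9.3 is that "Bowel cleansing assessment and gas measurement are available for all colon segments after standard washing and air insufflation for luminal distension". The synopsis (1.1) has the same criterion, worded as BBPS and H2 and CH4 "measurement are available for all colon segments after standard washing and air insufflation for luminal distension". Neither place makes an exception for equipment failure. The provision for sampling as near the ileocaecal valve as possible deals with anatomical obstacles, not with a lost reading.

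**FAS definition.** The FAS has no gas condition. Beyond intake of the preparation and a colonoscopy, it asks only that patients "have a BBPS available for at least one colon segment after standard washing and air insufflation for luminal distension".

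**Endpoint.** Adequate cleansing in 9.4.1 is a BBPS total of at least 6 with at least 2 in each segment. Gas plays no part in it.

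**Role of PP.** For the phase III primary analysis on FAS and PP, 9.4.1 states: "Results from both populations will have equal importance". For phase II it states: "Endpoints will be analysed on the PP population", with the FAS as support.

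**Gas analyses.** Section 9.4.2 places these elsewhere: "Descriptive statistics both on the Safety set and on the modified Safety set for both phase II and phase III will be performed on" a list that includes dangerous gas levels and gas concentrations.

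**Attrition.** Section 9.1 raises 626 patients to 696 "considering an expected rate of dropouts and major protocol deviations of about 10" per cent.

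**The concern.** A PP set should exclude patients who did not receive the treatment or assessment as planned. A patient who took the whole preparation, had a complete colonoscopy and was scored in all three segments has a valid primary outcome. A failed detector or catheter in one segment says nothing about adherence or about the BBPS, and PP already has separate criteria for completed treatment, adequate colonoscopy and significant violations.

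Two things are at stake. The first is precision: PP shrinks for a reason unrelated to cleansing. The second is selection. Gas is drawn through a catheter in the working channel (8.1.1), so residual stool or fluid could plausibly hinder a reading. If it did, PP would lose preparation failures preferentially, and a real deficit would look smaller. In phase II the same effect would raise the response rate that is compared with the 75% selection criterion.

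**Working it through.** **Inputs from the documents (9.1, 9.4.1).** Success rate 0.85 in both arms, margin 0.08, one-sided alpha 0.025, power 80%, 313 per group, 10% allowance, 348 randomised per group. **Assumed, because the documents give no figure:** the rate of missing gas readings and its relation to cleansing.

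**1. The plan's own figure.** n = (1.960 + 0.842)² × 2 × 0.85 × 0.15 / 0.08² = 312.7, so 313 per group. 626 / 0.90 = 695.6, so 696. Both reproduce.

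**2. Power if gas-only losses g come on top of the 10%.** n = 313 × (1 - g); SE = √(2 × 0.85 × 0.15 / n); power = Φ(0.08 / SE - 1.96).

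| Assumed g | n per arm | PP power |
|---|---|---|
| 0 | 313 | 80.0% |
| 2% | 306.7 | 79.2% |
| 5% | 297.4 | 78.0% |
| 10% | 281.7 | 75.8% |

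Three segments must each be read. With an assumed independent failure rate of 2% per segment, 1 - 0.98³ = 5.9% of patients would be lost.

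**3. Shift if missing readings depend on cleansing.** Let a reading be missing in a share a of adequate colons and b of inadequate ones. The PP success rate is p(1 - a) / [p(1 - a) + (1 - p)(1 - b)]. Take the non-inferiority boundary, 0.77 against 0.85, with a = 3%.

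Example for b = 10%:
- Test: 0.7469 / (0.7469 + 0.2070) = 0.7830.
- Standard: 0.8245 / (0.8245 + 0.1350) = 0.8593.
- Difference: -0.0763.

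The PP-alone one-sided error is Φ((difference + 0.08) / SE - 1.96), where the SE uses the PP rates and the patients retained out of 313 per arm. The margin is held at 0.08.

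| b | PP difference (true -8.0 points) | PP-alone error (nominal 2.5%) |
|---|---|---|
| 3% | -8.0 | 2.5% |
| 5% | -7.9 | 2.7% |
| 10% | -7.6 | 3.3% |
| 20% | -7.1 | 4.9% |
| 30% | -6.4 | 7.7% |

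**4. Phase II under the same model.** With a = 3% and b = 20%, a true response of 72% becomes 0.6984 / (0.6984 + 0.2240) = 75.7% in PP, which is above the 75% criterion.

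**The case against.** **The FAS contains the harm in phase III.** Every affected patient stays in the FAS. When the selection model in step 3 is simulated at the boundary, the chance that FAS and PP both show non-inferiority is about 2.1% for b = 10%, 20% and 30% alike. A reader might infer from the table that the trial's false-positive rate rises to 7.7%. The documents do not support that. The figure is for PP alone, and the plan gives the two sets equal importance without saying whether both must succeed or either may. It does not call them co-primary. This part of the objection stands.

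**The link to poor cleansing is conjecture.** A reader might also infer that failed readings are known to follow residual stool. No section reports failed readings or their cause, and the readings in question are taken after washing and insufflation. Within completed, fully scored examinations the differential could be mild, as in the 5% row, or absent. This also stands, and it makes step 3 an illustration and not an estimate.

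**The power loss may be smaller than shown.** The 10% may be meant to include missed measurements, since 10.1.8 counts any noncompliance as a deviation. Section 9.1 also provides for re-evaluating the sample size after phase II, when the missing-reading rate will be known. Both points are fair. A larger sample would restore power but would not remove a selection effect.

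**Completeness has a rationale.** Gas safety is a dose-selection criterion, so judging cleansing and gas in the same patients is understandable. But 9.4.2 places the gas results of both phases on the Safety sets, so the PP condition does not serve that purpose.

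**Conclusion.** The point holds as a defect of definition. The gas condition can remove valid cleansing outcomes from PP, and it serves no gas analysis that the plan describes. The size of the effect is unknown. On assumed extra losses of 2% to 10%, PP power falls from 80% to between about 79% and 76%, a modest loss that is smaller still if the 10% allowance already covers it. If missing readings are unrelated to cleansing, that is the whole cost.

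The shift of a true -8.0 points to between -7.6 and -6.4, with PP-alone error of about 3.3% to 7.7%, rests entirely on the assumed 3% against 10% to 30%. In phase III it would alter the conclusion only if PP by itself could carry the claim, which the plan leaves open. In phase II it would act directly on the lead set, although selection there is descriptive and also uses gas safety and clinical judgement.

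**What to change.** In 9.3 and in the synopsis (1.1), delete the gas-availability condition from the PP definition used for cleansing endpoints. PP would then require BBPS in all segments plus the existing criteria on completed treatment, adequate colonoscopy and significant violations. This also settles whether a missing O2 value excludes a patient, which is unclear because 9.3 refers to gas measurement in general while the synopsis names only H2 and CH4.

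Leave the gas analyses on the Safety and modified Safety sets as they stand, and do not add a complete-readings condition to them. Such a condition would be a complete-case restriction that 9.4.2 does not have, and it could drop a patient with a dangerous level in one segment and a missing reading in another.

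The cost is a wording change in two places. It needs no new data, visits or patients, and PP stays the same size or grows slightly. It should be made before unblinded results are seen, since removing the condition later could look data-driven.
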